6.0 STUDY DESIGN

6.1 Overview of Study Design

[figure not shown]

Figure 2: Study design. Additional information about the box in blue (identification and enrollment of study participants) can be found in Figure 1 above.

This is a 2-arm, multi-site, randomized, controlled trial evaluating the effectiveness of PILOT compared with TAU on the frequency of self-reported overdose risk behaviors at 180 days (6 months).

This study will be initiated in the Emergency Department (ED). In addition to routine ED medical care, all ED sites will have an operationalized peer support system in the ED that will serve as part of TAU (“TAU peer,” though it should be noted that TAU peers may not be available 24 hours/day).

After assessment and stabilization as part of routine TAU by ED staff, a member of the research team will approach patients who may qualify for the study, in-person or remotely, for screening, consent, and enrollment in the study. All study sites will have detailed procedures for proper identification and recruitment of study participants. All study sites will operate under the MUSC policies and procedures for recruitment given the SmartIRB master reliance agreement. As such, recruitment procedures will be the same across study sites, with any differences outside of the MUSC policies being specifically stated and approved as part of local study site standard operating procedures (SOPs). If the participant is eligible and interested, after consent and determination of eligibility, they will be randomized to either PILOT (in addition to continuing TAU) or to continue TAU at that time.

For participants randomized to PILOT, in addition to receiving TAU (including possible interaction with the TAU peer), there will be an “on-call” system for the PILOT intervention peers such that

they are available to come to the ED to connect with any recent overdose survivors randomized to PILOT, either in-person or remotely. If these procedures are completed remotely, HIPAA-secure videoconferencing and approved REDCap tele-consenting will be used, and options will exist to complete screening and consent after a patient is discharged from the ED, should the potential participant provide verbal consent to be contacted by research staff about the study later. Intervention participants will begin the PILOT intervention in the ED, in-person or remotely, following the PILOT intervention manual. PILOT will utilize a tiered approach to assertive community engagement, utilizing motivational interviewing and Strengths-Based Case Management approach to engage patients in care and develop a patient-centered wellness/recovery plan. The PILOT intervention will be tailored to the participant's needs (e.g., harm reduction, recovery, and treatment resources as they are interested and ready) and will involve contact and interaction with PILOT peers (details included in the PILOT intervention manual) over the course of the 180-day (6 month) treatment period. Participants randomized to TAU will continue TAU and receive any additional standard treatment provided at the respective ED for overdose survivors, including interaction with TAU peer as per hospital practice. All participants (TAU and PILOT) will, in the least, be provided with referral and community resource information, consisting of at least: (1) a handout providing names, locations, and telephone numbers of addiction treatment services in the area; (2) telephone access to call a clinician or facility of their choice, which will be informed by their method of healthcare coverage; and (3) information about receiving naloxone per state regulations and community resources. Addiction services can include a range of treatments with varying intensity and duration, based on local resources and patient preference. TAU peers will conduct their standard TAU protocol as they would for any other NFOO or substance use patient admitted to the ED, like what is described above as an SBIRT-like model common in hospital and ED settings with peer support services in place.

During the site selection process, a thorough assessment will be conducted of each site's standard practice for overdoses and substance-related issues in the ED and description of peer services will be provided and reviewed (See **Section 9.3**).

Throughout the course of the trial, sites will be monitored for any potential changes that might occur to TAU around providing resources and/or treatment to overdose survivors.

7.0 OUTCOME MEASURES

7.1 Primary Outcome Measure

The Primary Aim of this study is to compare the effectiveness of PILOT versus TAU in approximately 150 patients who are admitted to an ED after an NFOO or admitted to the ED with an SUD-related issue and self-report recent (past 30-day) NFOO on the primary outcome of the past month total score on the modified and expanded Overdose Risk Behavior Checklist, which captures the frequency of self-reported overdose risk behaviors, at 180 days (6 months). The study will use a modified and expanded version of an Overdose Risk Behavior Checklist (ORBC), adapted from Bohnert et al. (2016) [23]. This assessment has been adapted and is being used currently in a study focused on risk reduction in NFOO admissions to EDs (RELAY; NCT04317053). The ORBC that will be used in CTN-0107 is a 13-item scale, with 11 of the items used to generate a total score (ranging from 0-44); higher scores will indicate greater frequency and number of overdose risk behaviors. Some items have branching/sub questions, which are not included in the total score to allow for the same possible number of points for all study participants. These questions will measure risk behaviors in the past month, and the total risk score is an aggregation of responses to the specific individual questions.

7.1.1 Hypothesis 1 (Primary Outcome Measure):

The study hypothesis is that the PILOT intervention will result in reduced frequency of self-reported overdose risk behaviors (i.e., lower ORBC total score) via the ORBC at Day 180 after randomization compared to TAU.

7.2 Secondary Outcome Measures

The secondary outcomes of the study are: 1) number of steps achieved on a modified SUD Cascade of Care at 180 days (6 months) after Index ED admission; and (2) engagement with the study and PILOT intervention, measured by (a) the number of potentially eligible patients approached compared with the number willing to be enrolled and (b) the length of engagement and enrollment in PILOT among those randomized to PILOT. Length of engagement and enrollment is defined as the time from baseline to last meeting with the PILOT intervention/counselor.

Modified SUD Cascade of Care (Secondary Outcome Measure):

CASCADE	OD Identification & Harm Reduction	Engagement in Care		MOUD Initiation	MOUD Retention			Treatment Response & Remission (6 month)		
STEPS	1 ↑ Harm Reduction	2 Any Care	3 Regular Care	4 Any MOUD	5 MOUD X 1 mo	6 MOUD X 3 mo	7 MOUD X 6 mo	8 ↓ SUD Severity	9 Early Remission	10 ↑ Recovery Score
MEASURE	Harm Reduction Checklist	Step 2-7 Assessment Form (SAF 2-7)		SAF 2-7	SAF 2-7 AND MOUD Confirmation Form			DSM 5 Checklist Toxicology screen		Assessment of Recovery Capital Scale

Step Eligibility: All enrolled participants will be considered to have 0 steps achieved at the time of study entry (baseline). Acknowledging that individuals will vary in presence and types of SUD diagnoses, this pilot trial will evaluate the differing numbers of steps achieved in each sub-type of enrolled participant (primary OUD, primary SUD other than OUD, no identified SUD identified at baseline via administration of the DSM-5 checklist). A participant will be counted as having met a particular step if criteria are met at ANY study visit or for any length of time during the study, even if the participant subsequently does not endorse a previously endorsed item.

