2.0 STUDY SYNOPSIS

2.1 Study Objectives

The primary objective of this study is to advance understanding and improve outcomes for individuals who present to an Emergency Department (ED) after surviving a non-fatal overdose involving opioids (NFOO). To achieve this objective, the study will evaluate the preliminary effectiveness of a specialized, enhanced peer recovery intervention tailored for NFOO survivors, called Peer Intervention to Link Overdose Survivors to Treatment (PILOT), on self-reported overdose risk behaviors for individuals who present to the ED after a NFOO. The PILOT intervention will be compared to treatment as usual (TAU) in the ED setting.

The secondary objectives of the study are to: 1) evaluate the number of steps achieved along a modified Substance Use Disorder (SUD) Cascade of Care for individuals randomized to PILOT vs TAU, and 2) to assess whether NFOO survivors within an ED setting are willing to engage with overdose peer support using the PILOT model (feasibility).

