8.4 Strategies for Recruitment and Retention

Participants will be recruited from the ED at the time of ED admission (primary method of recruitment). Recruitment, approaching patients, screening, consent, and study procedures can be completed in-person or remotely, utilizing HIPAA-compliant videoconferencing and approved tele-consenting platforms as applicable. There will be two sources of referral: (1) During routine clinical care, patients presenting with or identified or suspected of having experienced an overdose in the past 72 hours, as identified by ED staff, including medical providers and TAU peers, can be referred for study screening; and (2) Research study staff will follow ED trackboards, coordinate with TAU peers and ED staff to screen for and identify individuals who may have experienced an overdose in the past 72 hours, and screen all SUD admissions for overdose in the past 30 days. This screening may include any individuals presenting with overdose or those who present with other substance use-related issues, including but not limited to, withdrawal, polysubstance use and consequences therein, and injection-related infection. The identification of an ED champion at each site will aid in successful recruitment and troubleshooting procedural or workflow issues with ED staff and providers. The study, including all study sites, will operate under the MUSC policies and procedures for recruitment given the SmartIRB master reliance agreement. As such, recruitment procedures will be the same across study sites, with any differences outside of the MUSC policies being specifically stated and approved as part of local study site standard operating procedures (SOPs).

8.4.1 Recruitment provisions for modified operations due to COVID-19, other population-level safety concerns, or low enrollment at sites:

8.4.1.1 *Remote Recruitment/Enrollment*

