A secondary outcome is the number of steps achieved along a modified SUD Cascade of Care. This will be modeled similar to the primary outcome, an over dispersed Poisson regression model with fixed effect covariates for treatment, site, and stratum. Note that no baseline score covariate is included as all participants will be considered to have achieved 0 steps at baseline. Similar to the primary outcome, a RR along with 95% confidence interval and p-value will be given from this model to determine the effect and significance of PILOT as compared to TAU.

An important point to consider is that participants entering the trial may not have a primary diagnosis of OUD, or even SUD. Because of this, some steps are not inherently eligible to them at baseline. However, during the study, the participant may endorse OUD, or some SUD if none were at baseline, and become eligible for these steps. The approach taken here for the prespecified analysis method is that of protection/balanced by randomization. Participants entering without OUD, or no SUD, are likely to be balanced between treatment groups due to random assignment to treatment group (based on baseline DSM-5 SUD diagnoses), such that the effects of this would be equal between PILOT and FORCE. Additional supportive analyses, such as looking at OUD, SUD other than OUD, and no SUD subgroups as determined at baseline, are possible to examine possible chance imbalance between PILOT and FORCE.

For the other secondary outcomes, the number of participants approached and number who were willing to engage with CPPSSs using the PILOT model, as well as percent of those approached who were willing to engage, will be summarized. A 95% confidence interval will be provided for this percent. The length of engagement with PILOT will be similarly summarized.

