## 2.0 SUMMARY OF STUDY DESIGN AND PROCEDURES

### 2.1 Study Objectives

The primary objective of this study is to advance understanding and improve outcomes for individuals who present to an Emergency Department (ED) after surviving a non-fatal overdose involving opioids (NFOO). To achieve this objective, the study will evaluate the preliminary effectiveness of a specialized, enhanced peer recovery intervention tailored for NFOO survivors, called Peer Intervention to Link Overdose Survivors to Treatment (PILOT), on self-reported overdose risk behaviors for individuals who present to the ED after a NFOO. The PILOT intervention will be compared to treatment as usual (TAU) in the ED setting. The secondary objectives of the study are to: 1) evaluate the number of steps achieved along a modified Substance Use Disorder (SUD) Cascade of Care for individuals randomized to PILOT versus TAU, and 2) to assess whether NFOO survivors within an ED setting are willing to engage with overdose peer support using the PILOT model (feasibility).

Exploratory objectives are to assess the effects of PILOT versus TAU on the magnitude of achievement on the modified SUD Cascade of Care, on initiation of Medication for Opioid Use Disorder (MOUD), on substance use frequency, on engagement in Peer Support Services, on self-reported attendance at a recognized recovery organization or formal SUD treatment, on the percentage of toxicology screens positive for primary substance use, and on repeat non-fatal overdose and rates of death (see Section 7.7).

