## **3.0 GENERAL ANALYSIS POPULATIONS, DEFINITIONS, AND CONVENTIONS**

### **3.1 Analysis Populations**

#### **3.1.1 Preliminary Screened Population**

The preliminary screened population consists of all participants who provided verbal consent and were evaluated for basic study eligibility criteria. Those found to be eligible at preliminary screening are captured under Segment A (ENRA form), whereas those not interested in participating or are ineligible and, if applicable, reasons for ineligibility, are captured under Segment Y (ENRY form).

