### **3.1.5 Approached Population**

The approached population consists of all individuals who were approached in the ED for possible participation in the study, including those who did and did not provide verbal consent for further assessment of eligibility.

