### 7.5.2 Engagement with the Study and PILOT Intervention

For engagement with the study and with the PILOT intervention, the number of participants approached (from SCA form) and number who were willing to engage with PILOT peers, as well as the percent of those approached who were willing to engage, will be summarized. A 95% confidence interval will be provided for this percent. The length of engagement with PILOT will be similarly summarized. The template SAS code for these two analyses is given below:

```
proc freq data = secondout_consented;
  tables consented / binomial(level = 'Yes' CL = wald);
  weight count;
run;
```

where:

- *secondout\_consented* is the summarized dataset containing numbers of participants who provided or did not provide written informed consent to participate,
- *consented* is a categorical variable which has "Yes" and "No" responses, with "Yes" being consented to participate in the study (EC0107A.S07CNSNT or EC0107Y.S07CNSNT), and

- *count* is the number of participants who provided the corresponding response, out of patients approached for the study (SCA.SCNPTAPR).

This analysis generates the binomial proportion (with Wald confidence limits) for those consenting to be in the study.

```
proc means data = secondout_length mean std p25 p50 p75 min max clm;  
  var length;  
run;
```

where:

- *secondout\_length* is the dataset containing for each participant in PILOT treatment arm the days since randomization for each peer intervention,
- *length* is the number of days between the randomization date and the last intervention for that participant, as indicated on the PIL form in PILOT treatment arm (PIL.PIENGACT, PI2.P2ENGACT, ..., PI7.P7ENGACT).

This analysis generates descriptive summary statistics (mean, standard deviation, quantiles, and range) for the duration of engagement in the PILOT intervention.

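### The willingness percentage divides by everyone approached and can count consent to screening as willingness, so it does not measure willingness among NFOO survivors

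*Protocol*

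**What the plan says.** - **Objective.** Both documents aim to "assess whether NFOO survivors within an ED setting are willing to engage with overdose peer support using the PILOT model (feasibility") (SAP 2.1, and Protocol 2.1 in the same terms).
- **Outcome.** Protocol 7.2 compares "the number of potentially eligible patients approached compared with the number willing to be enrolled". Protocol 14.4 summarises the "percent of those approached who were willing to engage", with a 95% confidence interval.
- **Denominator.** SAP 7.5.2 takes the count "out of patients approached for the study (SCA.SCNPTAPR"). SAP 2.2.2 describes this form as a weekly tally of patients approached so that eligibility and interest can be assessed. SAP 3.1.5 defines the Approached population as "all individuals who were approached in the ED for possible participation in the study", whether or not they agreed to be assessed.
- **Who is approached.** Under Protocol 8.4 staff take referrals of suspected overdoses and also "screen all SUD admissions for overdose in the past 30 days". Under Protocol 10.1 overdose questions come after verbal consent, and written consent comes after those questions.
- **Numerator.** SAP 7.4.2 and Table 36 define willing as verbal consent recorded on the ENRA or ENRY form. SAP 3.1.1 says that "those not interested in participating or are ineligible and, if applicable, reasons for ineligibility, are captured under Segment Y (ENRY form"). SAP 7.5.2 describes its dataset in terms of written informed consent, yet cites consent variables from the same two forms.

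**The concern.** The objective is about people who survived an opioid overdose. The percentage is taken over people whose overdose status was not known when they were counted. Shell Table 1 expects some of them to fail the NFOO criteria, to have had an intentional overdose, or to be in custody. None of these people could be enrolled, and neither document takes them out of the denominator.

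They then affect the result according to how the numerator is read. Under written consent they count as not willing. Under verbal consent on ENRY they can count as willing, as can patients who were not interested in taking part.

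This is a named secondary outcome of a pilot meant to inform a larger trial. Planners need to tell apart two situations: few of the patients approached were eligible survivors, or survivors were found and declined. The planned percentage cannot separate them.

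**Working it through.** The documents set no expected or target value for this percentage, so there is no planned figure to reproduce. The check is of the definitions, followed by the size of the distortion under stated assumptions.

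**Order of events (Protocol 10.1; SAP 2.2.2, 3.1.1, 3.1.5)**
1. Patient approached: counted in the denominator.
2. Verbal consent to screening: willing under SAP 7.4.2 and Table 36.
3. Overdose and other eligibility questions: ineligible or not interested goes to ENRY, eligible to ENRA.
4. Written consent: willing under the description in SAP 7.5.2.

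The denominator is fixed at step 1, and NFOO status is first asked at step 3.

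**Inputs.** The ineligible share *f*, the willingness *w* among eligible survivors and the number approached are not in the documents. All values below are assumptions.

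**Written-consent numerator.** If no ineligible patient signs, reported percentage = *w*(1 − *f*). With *w* = 70%:
- *f* = 20%: 0.70 × 0.80 = 56%
- *f* = 40%: 0.70 × 0.60 = 42%
- *f* = 60%: 0.70 × 0.40 = 28%

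The shifts are 14, 28 and 42 points. With 500 approached, the widest Wald half-width is 1.96 × √(0.5 × 0.5 / 500) = 4.4 points, so the confidence interval would not reveal the problem. As one full example, take 500 approached, *f* = 50% and *w* = 60%, which gives 250 eligible and 150 consents:
- over all approached, 150/500 = 30.0% (26.0 to 34.0)
- over eligible survivors, 150/250 = 60.0% (53.9 to 66.1)

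**Verbal-consent numerator.** Let *v*E and *v*I be the verbal-consent rates among eligible and ineligible patients.

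Reported percentage = (1 − *f*)*v*E + *f* *v*I = *v*E + *f*(*v*I − *v*E)

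- *f* = 40%, ineligible consent 10 points higher: 0.40 × 10 = 4 points too high.
- *f* = 50%, *v*E = 60%, *v*I = 50%: 0.30 + 0.25 = 55.0%, 5 points too low.
- *f* = 50%, *v*E = 60%, *v*I = 90%: 0.30 + 0.45 = 75.0%, 15 points too high.

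If the two rates are equal the shift is zero, but the figure is then consent to be screened, a different quantity from willingness to enrol.

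**The case against.** **Potentially eligible already limits the denominator.** The phrase describes status before the overdose questions. Protocol 6.1 does say staff approach patients who may qualify, and trackboards and referral filter to some degree. That may keep the ineligible share modest, but it does not remove ineligible patients.

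**Other tables cover it.** Shell Table 1 gives ineligibility counts by reason, Table 2 gives the percentage of eligible preliminary screens that were randomised, and a CONSORT diagram is planned. These help. Table 2's percentage, however, is not the prespecified outcome, has no planned interval and omits patients who refused verbal consent. Because ENRY takes the not-interested, it also appears to omit eligible patients who declined at preliminary screening.

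**Approached-to-enrolled yield is a legitimate planning figure.** This stands. It should be kept, under that name.

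**Some ineligibility is unwillingness.** This also stands. Table 1 lists refusal to provide a release of information, and unwillingness or inability to follow procedures, among the reasons for ineligibility. Subtracting everyone recorded as ineligible would delete unwilling survivors and inflate the result.

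**Stronger readings a reader might infer.**
- *The percentage mostly reflects how widely sites screen, or is always too low.* No ineligible share is given, and the direction is fixed only for written consent.
- *This is the main feasibility figure.* It has no target, and none of the four milestones in Protocol 7.4 uses it as its criterion.
- *A corrected rate could be set against the 98% in FORCE.* That figure (230/235, Protocol 4.2) is acceptance of a service, not consent to a randomised trial, and no comparison is planned.
- *Community recruits certainly distort the ratio.* The Approached population is ED-only, Table 1 has a community row and SAP 7.5.2 does not restrict the numerator. But community recruitment is contingent (Protocol 8.4.1.2), and SAP 2.2.2 does not expressly limit the approach count to the ED.

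**Conclusion.** The point holds. Followed exactly, the plan yields a percentage that combines eligibility with willingness and does not estimate willingness among NFOO survivors. This follows from the definitions and needs no assumed number.

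The size does rest on assumptions. Under written consent, an ineligible share of 20% to 60% would turn 70% into 56% to 28%. Under the verbal-consent definition in SAP 7.4.2, the distortion may be a few points or larger, in either direction. The primary outcome and the trial's power are not affected.

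**What to change.** In SAP 7.5.2 and Table 36:

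1. Keep the all-approached percentage, labelled as recruitment yield.
2. Add a willingness rate. **Numerator:** ED-recruited patients giving written informed consent. **Denominator:** ED-approached patients not found to fail the NFOO criteria or another non-volitional criterion (no opioid overdose in the window, intentional overdose, age, custody where recorded, medical or psychiatric inability).
3. Keep in the denominator, as not willing, those whose recorded reason is unwillingness: declined, not interested, release refused, unwilling to follow procedures. Assign ambiguous reasons, such as lacking two contacts or being unable to attend follow-up, in advance.
4. Apply the same restriction to numerator and denominator. Otherwise the ratio can exceed 100%: with 100 approached, 90 verbal consents and 50 of those ineligible, an unmatched ratio is 90/(100 − 50) = 180%.
5. Bound the effect of early refusers. With A approached, X excluded under item 2, R refusing before the overdose questions and C consenting (all ED), report C/(A − X) if all R are eligible and C/(A − X − R) if none are.
6. Reconcile verbal and written consent between SAP 7.4.2, SAP 7.5.2 and Table 36.
7. Report any community recruits separately. Footnote that re-screened patients cannot be linked and count as new people (SAP 4.1).

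The cost is SAP and table wording plus some analysis work. Ineligibility reasons and recruitment method are already recorded, with one doubt: Protocol 11.3.2 says no data are kept on prisoner encounters, while Table 1 has a custody row. The drawback is a range instead of a single figure, which could be wide if many patients refuse early.
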